4.1 Selection of Study Population

Email, plus referral from colleague? Nurses, doctors, others?

4.2 Inclusion Criteria

Front-line healthcare workers (how to make sure we get clinical staff who use PPE regularly?)

4.3 Exclusion Criteria

Healthcare workers with known skin allergies to povidone iodine.

4.4 Participant Withdrawal

Participants may withdraw from the study at any time. Any cultures collected from participants wishing to withdraw will be destroyed.

4.5 Participant Compensation

Upon completion of the two study arms, participants will receive a \$30 gift card to thank them for their time. Gift cards will be sent from the XXXXXX to participants via University of Iowa Campus Mail.

5 Informed Consent Process

5.1 Recruitment

Email? Referral?

Then set up appointment for consent – where will we do this? Lab?

5.2 Informed Consent Process

Participant meet with RA, go through consent form, questions, proceed immediately to pilot test. Whole thing take 2 hours?

6 Statistical Plan

6.1 Power Calculations

On the basis of the literature, we assumed that 80%-90% of participants will contaminate themselves with MS2 and 60%-70% with *S. marcescens*. If Provodine™ is effective, 20 participants in each group would provide 80% power to detect a 60%-70% relative decrease (rate ratio = 0.3 to 0.4) in the rate of self-contamination (present or absent) and higher power to find a significant difference in the quantity of MS2 or *S. marcescens* recovered from participants' hands.

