1.5 Risk Benefit Ratio

The potential benefits of this study outweigh the minimal risks to participants.

2 Study Objectives, Aims, and Hypothesis

Participants will serve as their own controls in this pilot study, first in a control arm then a Provodine™ arm.

Hypothesis: We hypothesize that Provodine™ will protect participants' hands from contamination with the test contaminants during PPE removal. Bacterial growth from the bag-broth cultures from the Provodine™ arm will have significantly less growth than from the control arm.

3 Study Design and Procedure

Study Design: We will perform a two-armed pilot test among 40 front-line healthcare workers (nurses, doctors, respiratory therapists, etc) at the University of Iowa Hospitals and Clinics. Participants will serve as their own controls. First, participants will perform hand hygiene with alcohol-based hand rub as they normally would in clinical practice then don PPE. We, the research team, will contaminate participating healthcare workers' (HCW) PPE with either bacteriophage MS2 (twenty participants) or *S. marcescens* ATCC 14756 (twenty participants). MS2 preparation and propagation and *S. marcescens* culture suspensions will each be performed as previously described.(123, 124) The MS2 bacteriophage will be suspended in 0.01 M phosphate-buffered saline and each PPE site will be contaminated with 105 plaque-forming units (PFU) of MS2 in 5 drops of 5 µL each. Aliquots of 3 mL of *S. marcescens* broth suspension (yielding bacterial titers of $\sim 1 \times 10^9$ CFU/ml) will be applied to each PPE site. Participants will then doff PPE using the Centers for Disease Control's (CDC) recommended protocol. We will sample their hands using the bag broth method. A research assistant will monitor participants as they wash their hands with soap and water then rinse their hands with 70% ethanol. Participants will then apply Provodine™ to their hands and put on (don) fresh PPE. We will repeat the contamination, doffing, and sampling procedure. For MS2 recovery, we will assay the eluent using the most probable number (MPN) enrichment infectivity assay.(126) For *S. marcescens* recovery, we will dilute the eluent, plate it, incubate the plates, and count the colonies as described.(124, 127)

4 Selection and Withdrawal of Participants

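### Section 6.1's 80% power for a rate ratio of 0.3 to 0.4 is not supported across the stated range for S. marcescens with 20 own-control pairs

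*Combined protocol and SAP*

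**What the plan says.** Section 6.1 (Power Calculations) assumes that "80%-90% of participants will contaminate themselves with MS2" and "60%-70% with *S. marcescens". It then states that "20 participants in each group would provide 80% power to detect a 60%-70% relative decrease (rate ratio = 0.3 to 0.4") in contamination scored as present or absent, and adds, without a calculation, that power for the quantity recovered would be higher.

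Section 3 (Study Design and Procedure) sets the design: "Participants will serve as their own controls", control condition first, with PPE contaminated by either "bacteriophage MS2 (twenty participants) or *S. marcescens* ATCC 14756 (twenty participants").

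Section 6.2 (Analytical Plan) names a paired t-test or Wilcoxon signed-rank test for the quantity recovered. It names no test for the present-or-absent outcome on which Section 6.1 bases its power. Neither section gives an alpha level, sidedness, a within-person correlation or discordant-pair rate, or says which rate ratio goes with which control rate.

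**The concern.** One power figure, "would provide 80% power", is attached to a range of effects and to four control rates (60%, 70%, 80% and 90% at the ends of the two ranges). Power cannot be the same over that grid, so the first question is where in it the figure holds.

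The second question is the design. Each organism has 20 people measured twice. A present-or-absent comparison is then a McNemar-type test on 20 pairs, and its power depends on the discordant pairs. A formula for two independent groups of 20 treats the 40 measurements per organism as coming from 40 people.

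This paragraph is the only justification of the sample size. If its figure is too high for one organism, readers will overrate what a non-significant present-or-absent comparison for that organism can exclude, should one be reported.

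**Working it through.** **Inputs.** From Section 6.1: control rates p1 of 60% and 70% (S. marcescens), 80% and 90% (MS2); rate ratio RR of 0.3 and 0.4, so p2 = RR × p1; n = 20 per organism. From Section 3: the same 20 people give both measurements. Assumed, because not stated: two-sided alpha 0.05, no dropout, within-person correlation phi = 0, with a range shown below.

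**Step 1: reproduce the plan's figure.** Unpaired pooled-variance z formula, with p̄ = (p1 + p2)/2:

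power = Φ{ [√n (p1 − p2) − 1.96 √(2 p̄(1 − p̄))] / √(p1(1 − p1) + p2(1 − p2)) }

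- 60% v 18% (RR 0.30): (1.878 − 1.352)/0.6226 = 0.845, power 80.1%.
- 70% v 26.95% (RR 0.385): (1.925 − 1.385)/0.6379 = 0.847, power 80.1%.
- 60% v 24% (RR 0.40): (1.610 − 1.368)/0.6499 = 0.372, power 64.5%.
- 70% v 28% (RR 0.40): (1.878 − 1.386)/0.6416 = 0.768, power 77.9%.

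So the stated range matches this formula if 0.3 goes with 60% and about 0.4 with 70%. It does not give 80% at RR 0.4 for either S. marcescens rate.

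**Step 2: power for 20 pairs.** Let p10 = p1(1 − p2) − c be the chance of contamination under control only, and p01 = (1 − p1)p2 − c under Provodine only, with c = phi √(p1(1 − p1)p2(1 − p2)). The number of discordant pairs D is binomial(20, p10 + p01). Given D, the number favouring Provodine is binomial(D, p10/(p10 + p01)). The exact test rejects when twice the binomial(D, ½) tail is at most 0.05; power sums over all outcomes.

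Example, 60% and RR 0.4 with phi = 0: p10 = 0.6 × 0.76 = 0.456 and p01 = 0.4 × 0.24 = 0.096. About 20 × 0.552 = 11 discordant pairs are expected, of which 20 × 0.096 = 1.9 go the wrong way. With 11 discordant pairs the exact test tolerates one (2 × 12/2048 = 0.012) but not two (2 × 67/2048 = 0.065). Power is 50.0%.

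Power (%), phi = 0, two-sided 5%:

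| Organism | Control rate | RR | Unpaired z | Exact McNemar | Mid-p McNemar |
|---|---|---|---|---|---|
| S. marcescens | 60% | 0.3 | 80.1 | 67.4 | 76.2 |
| S. marcescens | 60% | 0.4 | 64.5 | 50.0 | 60.1 |
| S. marcescens | 70% | 0.3 | 90.7 | 81.1 | 87.3 |
| S. marcescens | 70% | 0.4 | 77.9 | 64.5 | 73.5 |
| MS2 | 80% | 0.3 | 97.2 | 91.8 | 95.1 |
| MS2 | 80% | 0.4 | 89.5 | 79.5 | 86.1 |
| MS2 | 90% | 0.3 | 99.7 | 98.2 | 99.1 |
| MS2 | 90% | 0.4 | 97.1 | 92.5 | 95.7 |

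The asymptotic McNemar test agrees with mid-p to within 0.1 point here.

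**Step 3: vary the correlation.** S. marcescens, RR 0.4, power (%) at control 60% / 70%:

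| phi | Exact | Mid-p |
|---|---|---|
| −0.2 | 43.1 / 56.6 | 52.8 / 66.0 |
| 0 | 50.0 / 64.5 | 60.1 / 73.5 |
| 0.2 | 59.5 / 75.4 | 70.4 / 83.7 |
| maximum (p01 = 0) | 78.3 / 90.8 | 89.9 / 96.5 |

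In the last row every discordant pair favours Provodine, and their number is binomial(20, p1 − p2). The exact test then needs at least 6, mid-p at least 5 and the asymptotic test at least 4. The asymptotic figures are 96.3 / 99.0.

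**Step 4: one-sided 5%, phi = 0, RR 0.4.** Exact McNemar 62.8% / 76.3%; unpaired z 76.1% / 86.8%.

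**The case against.** The best defence is that the sentence describes detectable effects: at 80% power the detectable ratio runs from 0.30 at 60% to about 0.385 at 70%, which the usual two-proportion formula confirms. On that reading there is no slip of arithmetic. This stands as an account of where the figure came from. But Section 6.1 does not state that mapping, and the formula belongs to independent groups. Under the same mapping (60% with 0.3, 70% with 0.4), paired power with no correlation is 67% and 65% (exact) or 76% and 74% (mid-p).

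It is also fair that zero correlation is an assumption. The same person doffs twice with the same contaminant and procedure, so positive correlation is plausible, and with enough of it 80% is attainable at a ratio of 0.4. The plan neither states nor justifies such a correlation.

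Four stronger readings are tempting, and the documents do not support them:

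- That 80% fails for S. marcescens throughout. At 70% and a ratio of 0.3, both the exact (81%) and mid-p (87%) tests reach it.
- That power at 0.4 simply is 50% to 65%. That needs an exact two-sided test and zero correlation, and the plan specifies neither.
- That 78% is a ceiling at 60% and 0.4 even with maximum correlation. It is the exact test's figure; mid-p gives 89.9% and the asymptotic test 96.3%.
- That a null S. marcescens result will be misread as excluding a 60% reduction. This is a pilot, and Section 6.2 plans no present-or-absent test, so that harm is only possible.

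**Conclusion.** The concern holds in a limited form. For S. marcescens, 80% power is not supported over the whole stated range of control rates and ratios. At a ratio of 0.4, every two-sided 5% calculation above that assumes independence falls short, from 50.0% (exact McNemar, 60% control) to 77.9% (unpaired z, 70% control). At 0.3 the paired tests fall short at a 60% control rate and pass at 70%. MS2 is not affected in substance: its lowest figure under independence is 79.5%.

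The sizes rest on a two-sided 5% level, 20 complete pairs and zero within-person correlation, none of which the plan states. Because the remedy is one of reporting and the planned tests concern quantity, this should be fixed but does not call the study into question.

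**What to change.** Rewrite Section 6.1 separately for each organism, for 20 pairs. State:

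- the paired binary test (exact or mid-p McNemar), and add it to Section 6.2 if the present-or-absent comparison is to be reported;
- alpha and sidedness;
- which control rate goes with each rate ratio;
- the assumed within-person correlation, with a range.

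Replace the flat 80% for S. marcescens with the resulting power: for example, at a ratio of 0.4 under independence, 50% to 65% (exact) or 60% to 74% (mid-p) as the control rate goes from 60% to 70%. Alternatively, give the largest ratio detectable with 80% power. For the exact two-sided 5% test under independence this is about 0.22 at a 60% control rate, 0.31 at 70%, 0.40 at 80% and 0.50 at 90%.

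The cost is one rewritten paragraph and a less favourable figure for S. marcescens. No participants are added.

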6.2 Analytical Plan

We will use the paired t-test or Wilcoxon signed-rank test to compare the quantity of MS2 bacteriophage or *S. marcescens* recovered after participants who applied Provodine™ to their hands before donning gloves with the quantity recovered from the control arm where participants who did hand hygiene with an alcohol-based product before donning gloves.

7 Data Collection, Handling, and Storage

All data collected will be stored in an electronic database on a shared drive within the University of Iowa Healthcare servers. Only members of the research team will have access to the database. No PHI will be collected. All participants will be identified in the database by a study number.

We will bank the isolates so that we can do susceptibility testing and pulsed field gel electrophoresis (PFGE) on the isolates in the future if this information is deemed important. All cultures and isolates will be labelled with study numbers and stored in XXXXXXXXX in the [name] lab.
